4.2 Inclusion/Exclusion Criteria for Psoriatic Patients

Inclusion Criteria

1. Group 1: Subjects with a history of moderate to severe psoriatic disease
2. Age ≥ 18 & < 90
3. Able and willing to provide written informed consent for the study

Exclusion Criteria

1. Unable to speak Spanish or English
2. Active smoking (within the past year)
3. Autoimmune, rheumatologic or inflammatory disease which are not psoriasis or psoriatic arthritis
4. Known active cancer receiving treatment
5. Pregnancy
6. Anemia (hemoglobin < 9 mg/dl) or thrombocytopenia (Platelet count < 75), or thrombocytosis (Platelet count > 600)
7. A history of severe bleeding or bleeding disorders
8. Current medication use which interact with either aspirin or atorvastatin
9. Chronic kidney disease (CrCl < 30 ml/min)
10. Congestive heart failure
11. Currently taking aspirin or a statin.
12. NSAID use within the past 48 hours

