4.4 Informed consent

If a subject wishes to participate, a member of the research team will review the informed consent documents, answer any questions, and obtain written consent for participation in the study and obtain written consent for future analysis, contact, and sample storage. Subjects will be given a "Subject history form" to fill out asking for a complete medical history. They will also be given an appointment reminder sheet to bring with their consent form. They will bring the subject history form to their first baseline assessment appointment. Participants will consent to complete the baseline assessments (see table 1). Participants may opt to decline participation in any baseline assessment they feel uncomfortable with or time constraints do not allow. Follow-up assessments will be completed in those who agree to aspirin or atorvastatin usage for the longitudinal part of the analysis. Participation in follow-up assessment is not required for participation in the baseline assessment. The consent process will take place in private offices at the NYU FGP, CTSI, ambulatory care center, Seligman Center for Advanced Therapeutics and Bellevue adult clinics. Subjects will be given the opportunity to be contacted for future studies that they may qualify for as well. A member of the research team will conduct the baseline interview with the subject and review the clinical history, demographic information and medication use with the individual. All information including the consent will be kept under double lock and key at the PI's office in NYU Skirball 9th floor.

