4.5.2 Longitudinal component (Group 1 only)

After baseline assessment, those with moderate to severe psoriatic disease will be offered by the study physician randomly the opportunity for longitudinal follow up and to take either aspirin and/or atorvastatin. For 2 weeks +/- 4 days, 1/4th of the subjects enrolled will be offered 81mg of aspirin, 1/4th of the subjects enrolled will be offered atorvastatin 40mg, ¼ will be offered both aspirin and atorvastatin and 1/4th will be offered nothing. Participants will be given the opportunity to only participate in the baseline assessment and opt out of the opportunity to take aspirin and/or atorvastatin and longitudinal component.

Both aspirin and atorvastatin are routinely used and approved in medical practice for the primary prevention of coronary artery disease. These medications are frequently used in the psoriatic population based on national guidelines when a calculated cardiac risk score is elevated (considered at moderate to high risk of cardiovascular events). These medications will be obtained from the Tisch outpatient pharmacy. They will be stored and dispensed with CTSI oversight. A drug accountability and storage log will be kept as per NYU research protocol.

A follow up assessment will be planed (table 1) at 2 weeks +/- 4 days and will include repeat blood draw (60 ccs, for the use of platelet function testing, biospecimen collection) and repeated endothelial vein harvesting. The end of the study is considered when the subject completes the follow up assessment. All study drugs will be stopped at this time. If the subject wishes to continue the study drugs they will be referred to their primary medical provider for further management.

A subject will be able to opt out of any part of the follow up assessment they desire. If a subject agrees to be started on aspirin and/or atorvastatin for the longitudinal part of the analysis and therapy for psoriasis is planned by the referring provider, we will attempt to perform the longitudinal follow up prior to their starting medication. Participation in this study will not impact planned treatment of the subjects by their primary provider.

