All subjects may be asked to provide additional information about their medical history, update any interim history and provide additional samples as noted above. Health information will be monitored overtime by review of the medical chart. Additional questions may be asked by phone or during routine clinical follow-up, as appropriate.

Table 1. Patient Group		Baseline	Longitudinal Analysis	Follow-up
1 n = 40	Moderate to severe psoriatic disease	1) Blood 2) Endothelial vein harvesting 3) Vascular function imaging	Offered: 1) Aspirin 2) Atorvastatin	1) Blood 2) Endothelial vein harvesting 3) Additional medical history

				obtained
2 n = 10	Healthy Controls	1) Blood 2) Endothelial vein sampling 3) Vascular function imaging		1) Additional medical history obtained

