4.5.4 Endothelial cell harvesting

There will be a maximum of two time points for endothelial cell harvesting and biospecimen collection. Endothelial harvesting will take place either in the CTSI or in the NYU Seligman Center for Advanced Therapeutics. Both of these centers have access to nursing support and ancillary support staff including trained phlebotomists. All subjects will have their blood drawn and endothelial harvesting after informed consent and completion of the screening interview. If willing to the subjects will be preferably fasting > 4 hours and water intake is allowed. They will be in a reclined position with feet elevated. An angiocatheter ≤ 21 gauge will be inserted into a peripheral vein on the upper extremity using aseptic technique. A 0.021in. diameter J-shaped wire (Daig, Minnetonka, MN) or a 0.018in. diameter J-shaped wire (Arrow, Reading, PA) will be then advanced into the angiocatheter, to a distance of 4cm beyond the end of the angiocatheter. Angiocatheters and J shaped wire described above are routinely used for intravenous fluids and medication administration in this hospital. Venous endothelial cells will be scraped from the intimas of superficial forearm veins by repeated (3 times) insertion and removal of the wire. The distal portion of the wire will be transferred to a 50ml conical tube containing dissociation buffer (0.5% bovine serum albumin, 2 mM EDTA, and 100 microg/ml heparin in PBS, pH 7.4) and maintained at 4°C until study. Half of retrieved endothelial cells will be used for RNA extraction and a half for immunofluorescence.

The angiocatheter used will be a ≤ 21 gauge (typically 20 gauge) INSYTE autoguard IV catheter which is routinely used for clinical care, IV hydration and administration of medications. In this case we will using this angiocathter off label as a method to safety access the peripheral vein. This poses a non-significant risk for the device according to 21 CFR 812.3 (m) because: 1) There is NO implantation of the device. 2) This device will not be used to sustain human life and does not pose a serious risk to health or safety of the subject. 3) This device will not be used to diagnose, cure, mitigate or treat a disease. 4) This angiocatheter device is routinely used across the country in clinics and hospitals and does not pose a serious risk to health, safety or welfare of the subject.

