We will evaluate the association between moderate to severe psoriatic disease and measures of thrombotic risk. As in Aim1, linear and nonlinear regression models will be employed to investigate the difference in platelet activity between those with and without psoriasis. This is gauged by monocyte platelet activity (MPA) and assessing monocyte – platelet interaction after adjusting for other covariates and applying model selection procedures. We will collect data including maximal aggregation (%), slope of the aggregation curve, and elapsed time between addition of agonist and onset of aggregation (lag phase). Regression models will unveil how these characteristics are influenced by those exposed to psoriatic disease, adjusting for other covariates.

c. Aim 3

We will then investigate how traditional medications used in CVD prevention such as aspirin and statins affect vascular function and thrombotic risk in those with moderate to severe psoriatic disease. We will assess baseline endothelial vein transcriptome data, genetic expression for routine markers of endothelial activation such as VCAM-1, ICAM-1, NF-kB and platelet reactivity data. Using paired t- tests, we will assess the changes to platelet reactivity and endothelial function with the use of aspirin, aspirin plus atorvastatin or atorvastatin therapy.

11. Safety and Adverse Events

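### Aim 3 names only before-and-after tests within the three drug groups; it uses neither the untreated quarter nor any between-arm comparison

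*Combined protocol and SAP*

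**What the plan says.** - **Design (Section 4.5.2).** After baseline, Group 1 (n = 40) is randomly offered one of four options. Two quarters are offered a single drug; of the rest, "¼ will be offered both aspirin and atorvastatin and 1/4th will be offered nothing". Follow-up is at 2 weeks, plus or minus 4 days.
- **Question (Section 3.3; Section 10, Aim 3; Section 6).** Aim 3 asks how the drugs affect vascular function and thrombotic risk. The Benefits section speaks of how treatment will improve the markers.
- **Analysis (Section 10, Aim 3).** "Using paired t- tests, we will assess the changes to platelet reactivity and endothelial function with the use of aspirin, aspirin plus atorvastatin", or with atorvastatin alone. The quarter offered nothing is not mentioned. The regressions under Aims 1 and 2 compare patients with healthy controls, not drug arms.
- **Power (Section 9).** With 10 per group, measured before and after, and d = 0.8, the plan claims 74% power at alpha 0.05 for a difference between groups. It names no test, sidedness, SD scale or correlation.
- **Who is followed.** Section 4.4: "Follow-up assessments will be completed in those who agree to aspirin or atorvastatin usage for the longitudinal part of the analysis". Table 1 has one row for Group 1 ("Offered: 1) Aspirin 2) Atorvastatin") and lists follow-up blood and vein harvesting for the group as a whole. The two do not agree on the untreated quarter.

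**The concern.** A paired test asks whether an arm changed from baseline. It does not ask whether the arm changed more than it would have without the drug. Three separate within-arm p-values also do not compare any arm with another. The question is causal and the design contains a random comparison that could answer it, but the named analysis leaves that comparison out.

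The documents leave room for change that is not due to the study drugs:

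- Psoriasis therapy may begin between visits; the protocol says only that "we will attempt to perform the longitudinal follow up prior to their starting medication".
- "NSAID use within the past 48 hours" is an exclusion at entry, but nothing repeats it for the follow-up visit.
- Fasting is optional: "If willing to the subjects will be preferably fasting" for more than four hours.

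The documents do not say that any of these moves the markers, or by how much. At stake are the trends that Section 9 wants to carry into further proposals: a within-arm trend alone does not show that the drug produced it.

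**Working it through.** **Inputs.** From the documents: 10 per arm (40 / 4), d = 0.8, alpha 0.05, stated power 74%. Assumed: the sizes of any non-drug shift and the baseline-to-follow-up correlation rho (0.2, 0.3, 0.46, 0.7). The value 0.46 is the only day-to-day reliability given (Section 4.5.3). It is for flow-mediated dilatation, which is not among the listed follow-up tests.

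**1. The plan's own figure.** Noncentral t at d = 0.8:

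| Test | Noncentrality | df | Two-sided | One-sided |
|---|---|---|---|---|
| Paired, n = 10 | 0.8 × √10 = 2.53 | 9 | 61.6% | 75.4% |
| Two-sample, 10 v 10 | 0.8 × √5 = 1.79 | 18 | 39.5% | 53.0% |
| Two-sample, 20 v 20 | 0.8 × √10 = 2.53 | 38 | 69.3% | 79.9% |

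The stated 74% is close to a one-sided paired test. It is also close to two between-arm calculations: a 20 v 20 analysis of covariance (ANCOVA) at rho = 0.3 (73.3%), and a four-group repeated-measures between-groups F test with assumed f = 0.4 and rho = 0.2 (λ = 0.4² × 40 × 2 / 1.2 = 10.67; df 3 and 36; 74.0%). The figure therefore does not identify a test.

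**2. Paired test with no drug effect.** If a non-drug shift equals s SDs of change, the noncentrality is s√10 with 9 df:

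| Assumed shift s | Paired test significant (two-sided) |
|---|---|
| 0 | 5.0% |
| 0.1 | 5.9% |
| 0.3 | 13.6% |
| 0.5 | 29.3% |

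**3. Between-arm test, same conditions.** Simulation, 40,000 trials per cell, 10 per arm, rho 0.2, 0.46 and 0.7, shift common to all arms. The four-arm ANCOVA (follow-up on baseline, aspirin yes/no, atorvastatin yes/no) rejects in 4.7% to 5.2% of trials per drug at every shift. With no shift the two methods do not differ per test.

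**4. Power of the between-arm test.** Each drug's margin is 20 v 20, with 40 − 4 = 36 df. The residual SD is the raw SD × √(1 − rho²), and the SD of change is the raw SD × √(2(1 − rho)). So the standardised effect is d/√(1 − rho²) if d is in raw SDs, or d√(2(1 − rho))/√(1 − rho²) if d is in SDs of change. Multiply by √10 for the noncentrality. Two-sided, d = 0.8:

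| rho | d in raw SDs | d in SDs of change |
|---|---|---|
| 0.2 | 71.0% | 88.8% |
| 0.3 | 73.3% | 86.3% |
| 0.46 | 79.2% | 82.2% |
| 0.7 | 93.1% | 76.1% |

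**5. If the untreated quarter is not followed.** Three arms, 10 v 10 contrasts, 30 − 4 = 26 df: 42.0%, 49.2% and 67.4% (raw SDs) or 60.4%, 52.2% and 46.4% (SDs of change) at rho 0.2, 0.46 and 0.7. A common shift cancels here too (simulated rejection 4.8% to 5.3%).

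**6. Limits of the between-arm test.** If shifts differ between the two margins by an assumed 0.1, 0.2 or 0.3 SD of change, the 20 v 20 ANCOVA rejects with no drug effect in 6% to 7%, 10% to 12% or 17% to 22% of trials (rho 0.2 to 0.7). With an assumed 7 completers per arm (14 v 14, 28 − 4 = 24 df), power is 55% to 81% (raw SDs) or 60% to 75% (SDs of change).

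**The case against.** **The comparator may not be measured.** Read with Section 4.4, the quarter offered nothing may have no two-week data, and leaving it out of Aim 3 would then follow from the visit schedule. This stands as an ambiguity. It does not excuse the lack of a between-arm test, because the three drug arms can still be compared with each other.

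**Not every shift is common to all arms.** The attempt to finish follow-up before psoriasis therapy starts is stated only for those who agree to a study drug. A shift could therefore fall mainly on the untreated arm, and the ANCOVA would not cancel it. Simulations with an assumed shift in that arm alone give rejection in about 7% to 9% of trials per drug at 0.3 SD of change, and about 12% to 17% at 0.5. This stands as a limit on the remedy. It remains less than the 13.6% and 29.3% that the paired test gives when the same shift falls on the arm it tests.

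**The shift sizes are assumed.** They are. Optional fasting, for instance, might add only noise. The logical gap does not depend on the sizes.

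**Section 9 speaks of a difference between groups.** That suggests the intent, so the gap may be under-specification. But no such test reaches Section 10, and the 74% does not settle which test was meant.

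**It is a pilot.** It is, and it makes no confirmatory claim. That limits the weight of the point. Nor is ANCOVA the only valid remedy: comparing changes between arms would also answer it.

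**Conclusion.** The concern holds. Four options are offered at random, the Aim 3 analysis covers three of them one at a time, and nothing else in the document supplies a between-arm comparison. Followed as written, the plan cannot attribute a change to a drug.

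How much this matters depends on non-drug change of unknown size. It costs nothing per test if there is none, and raises the rejection rate from 5% to 29.3% per test at an assumed 0.5 SD of change. The between-arm remedy holds 5% only for shifts shared by the arms. If all 40 complete, it need not lose power against the two-sided paired test (61.6%). Main effects assume no strong aspirin-by-atorvastatin interaction. The comparison is also open to selection, because the offer is not masked and "A subject will be able to opt out of any part of the follow up assessment they desire". This should be fixed, at modest cost, and does not undermine the pilot as a whole.

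**What to change.** 1. Make the main Aim 3 analysis a between-arm comparison by allocated group: one ANCOVA per marker, follow-up value on baseline value, aspirin (yes/no) and atorvastatin (yes/no), reported as estimates with confidence intervals. Make the interaction secondary and within-arm changes descriptive.
2. Reconcile Section 4.4 with Section 4.5.2 and Table 1 on whether the untreated quarter has the two-week assessment. If it does not, compare both drugs with atorvastatin alone (for aspirin) and both drugs with aspirin alone (for atorvastatin).
3. Restate the Section 9 power with its contrast, sidedness and SD scale, so that Sections 9 and 10 describe the same test.
4. Report the numbers allocated, accepting and completing in each quarter.

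**Cost.** If the untreated quarter is already followed: analysis wording and one power sentence, with no new data. If it is not, there are two routes. Adding the visit for about 10 patients means a second blood draw and vein harvest for each. The fallback contrasts need no new visit but have lower power (42% to 67% or 46% to 60%, depending on the SD scale).

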11.1 Definitions

Unanticipated Problems Involving Risk to Subjects or Others

Any incident, experience, or outcome that meets all of the following criteria:

- Unexpected in nature, severity, or frequency (i.e. not described in study-related documents such as the IRB-approved protocol or consent form, the investigators brochure, etc)
- Related or possibly related to participation in the research (i.e. possibly related means there is a reasonable possibility that the incident experience, or outcome may have been caused by the procedures involved in the research)
- Suggests that the research places subjects or others at greater risk of harm (including physical, psychological, economic, or social harm).

Adverse Event

An **adverse event** (AE) is any symptom, sign, illness or experience that develops or worsens in severity during the course of the study. Intercurrent illnesses or injuries will be regarded as adverse events. Abnormal results of diagnostic procedures are considered to be adverse events if the abnormality:

- results in study withdrawal
- is associated with a serious adverse event
- is associated with clinical signs or symptoms
- leads to additional treatment or to further diagnostic tests
- is considered by the investigator to be of clinical significance

Serious Adverse Event

Adverse events are classified as serious or non-serious. A ***serious adverse event*** is any AE that is:

- fatal
- life-threatening
- requires or prolongs hospital stay
- results in persistent or significant disability or incapacity
- a congenital anomaly or birth defect
- an important medical event

Important medical events are those that may not be immediately life threatening, but are clearly of major clinical significance. They may jeopardize the subject, and may require intervention to prevent one of the other serious outcomes noted above. For example, drug overdose or abuse, a seizure that did not result in in-patient hospitalization, or intensive treatment of bronchospasm in an emergency department would typically be considered serious.

All adverse events that do not meet any of the criteria for serious will be regarded as ***non-serious adverse events***.

Adverse Event Reporting Period

The study period during which adverse events will be reported is the period from the initiation of any study procedures to the end of the study treatment follow-up. For this study, the study treatment follow-up is defined as 5 days following the last administration of study treatment.

Preexisting Condition

A preexisting condition is one that is present at the start of the study. A preexisting condition will be recorded as an adverse event if the frequency, intensity, or the character of the condition worsens during the study period.

General Physical Examination Findings

At screening, any clinically significant abnormality will be recorded as a preexisting condition. At the end of the study, any new clinically significant findings/abnormalities that meet the definition of an adverse event will be recorded and documented as an adverse event.

Post-study Adverse Event

All unresolved adverse events will be followed by the investigator until the events are resolved, the subject is lost to follow-up, or the adverse event is otherwise explained. At the last scheduled visit, the investigator will instruct each subject to report any subsequent event(s) that the subject, or the subject's personal physician, believes might reasonably be related to participation in this study. The investigator will notify the IRB of any death or adverse event occurring at any time after a subject has discontinued or terminated study participation that may reasonably be related to this study.

Abnormal Laboratory Values

A clinical laboratory abnormality will be documented as an adverse event if any one of the following conditions is met:

- The laboratory abnormality is not otherwise refuted by a repeat test to confirm the abnormality
- The abnormality suggests a disease and/or organ toxicity
- The abnormality is of a degree that requires active management; e.g. change of dose, discontinuation of the drug, more frequent follow-up assessments, further diagnostic investigation, etc.

Hospitalization, Prolonged Hospitalization or Surgery

Any adverse event that results in hospitalization or prolonged hospitalization will be documented and reported as a serious adverse event unless specifically instructed otherwise in this protocol. Any condition responsible for surgery should be documented as an adverse event if the condition meets the criteria for an adverse event.

Neither the condition, hospitalization, prolonged hospitalization, nor surgery are reported as an adverse event in the following circumstances:

- Hospitalization or prolonged hospitalization for diagnostic or elective surgical procedures for a preexisting condition. Surgery will **not** be reported as an outcome of an adverse event if the purpose of the surgery was elective or diagnostic and the outcome was uneventful.
- Hospitalization or prolonged hospitalization required to allow efficacy measurement for the study.
- Hospitalization or prolonged hospitalization for therapy of the target disease of the study, unless it is a worsening or increase in frequency of hospital admissions as judged by the clinical investigator.

11.2 Recording of Adverse Events

At each contact with the subject, the investigator will seek information on adverse events by specific questioning and, as appropriate, by examination. Information on all adverse events will be recorded immediately in the source document, and also in the appropriate adverse event module of the case report form (CRF). All clearly related signs, symptoms, and abnormal diagnostic procedures results should be recorded in the source document, though should be grouped under one diagnosis.

All adverse events occurring during the study period will be recorded. The clinical course of each event should be followed until resolution, stabilization, or until it has been determined that the study treatment or participation is not the cause. Serious adverse events that are still ongoing at the end of the study period must be followed up to determine the final outcome. Any serious adverse event that occurs after the study period and is considered to be possibly related to the study treatment or study participation should be recorded and reported immediately.

